Demographics	Х													
TB screening ⁹	Х													
DPD deficiency screening ¹⁰	X													
UGT1A1 mutation screening 11	X													
Height	X													
Weight ¹²	X	Х	Х			X		Х			Х	Х		
Physical examination	X											Х		
Symptom-directed exam ¹³		Х	Х	[X]	[X]	Х	[X]	Х	[X]	[X]	Х			
Vital signs ¹⁴	X	X	Х	Х	Х	Х	Х	Х	Х	Х	Х	Х	Х	
Performance status 15	X	X	X			Х		Х			Х	Х		
HRQoL ¹⁶	X					Х		[X]			[X]	Х		Х
Concomitant medications 17	X	Х	Х	Х	Х	Х	Х	Х	X	Х	Х	Х	Х	
Adverse events 18		Х	Х	Х	Х	Х	X	Х	Х	Х	Х	Х	Х	
ECGs 19	X	Х	Х			Х		[X]				Х		
Hematology ²⁰	X	Х	Х			Х		Х			Х	Х	Х	
Chemistry ²¹	X	Х	Х			Х		Х			Х	Х	Х	

Page 16 of 127 Version: 2.0 Date: 22 JAN 2024

Treatment cycle (14 d)	SCR 2	Cycle 1		Cycle 2	2	су	cle 3	c	ycle 4-12		BNT321 monotherapy Cycle 13-24 ³	EOT 4	Safety FU ⁵	Survival FU 6
Days ¹		1	1	3	8	1	3	1	3	8	1			S
Serum amylase 22		Х	Х			Х		Х			Х	Х		
Serum lipase ²²		Х	Χ			Х		Х			Х	Х		
Haptoglobin ²²		Х	Х			Х		Х			Х	X		
GGT ²³	Х	Х	Х			Х		Х			Х	X		
Urinalysis ²⁴	Х													
Urine pregnancy test ²⁵	Х	Х	Х			X		Х			Х	X		
CA19-9 ²⁶	Х	Х		Х	Х		Х	[X]**	X**		X**	Х		Х
Pharmacokinetics 27				X	Х		Х	[X]**	X**		X**			
Disease assessment 28	Х							Х			Х	Х		X
Anti-drug antibody ²⁹		Х				Х		[X]				Х		
ADCC, CDC, and cytokines 30		X		X	Х				Х	X	Х			
Tumor biopsy ³¹	Х											[X]		
ctDNA 32		Х						[X]			Х	Х		
Randomization ³³	X 33													
BNT321 administration ³⁴				Х			Х		X		Х			
mFOLFIRINOX administration 35		Х	Х			Х		Х						
Survival status ⁶														Х

X - Required, [X] - Optional, or not with every visit

^{** -} Every fourth cycle (e.g., Cycle 4, Cycle 8, Cycle 12 etc.)

Clinical Trial Protocol BNT321-02

BioNTech SE Confidential

Version: 2.0 Date: 22 JAN 2024

Page 17 of 127

- 1. Window for all procedures, except those performed on Day 3 of all cycles, is ±3 days of the scheduled day. Day 3 procedures are performed without window.
- 2. Screening visit performed within 21 days prior to Cycle 1 Day 1 and may be repeated within 7 days of C1D1 if requested by Medical Monitor (e.g., borderline eligibility or clinical instability).
- 3. BNT321 monotherapy will continue every two weeks on Day 1 of every cycle for an additional 12 cycles to complete the adjuvant therapy course.
- 4. End of treatment (EOT) visit will be performed on the day the decision is made to discontinue BNT321 administration or at the completion of 24 cycles of therapy.

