- 15. Performance status must be recorded as ECOG and will be performed at screening, Day 1 of every cycle, at EOT, and as needed according to investigator's discretion based on new symptoms and/or medical concerns. Refer to the Appendix 1 for conversion between ECOG and KPS.
- 16. HRQoL will be performed at screening. Day 1 of every other treatment cycle starting from Cycle 3 to 24, at EOT, and at every disease assessment (see Footnote 28 for timing of disease assessments).
- 17. Recorded from 21 days prior to the first administration of BNT321 to EOT or safety FU visits. Includes prescription medications, over-the-counter medications, and supplements.
- Adverse events will be collected and reported from the signing of the trial-specific ICF until safety FU.
- 19. ECGs will be performed at screening and on Day 1 of every cycle for C1 through C3. On these days ECGs are obtained prior to treatment, at t_{max}, and at end of last mFOLFIRINOX infusion. Investigators may obtain ECGs at additional timepoints in Cycle 4 to 12 if indicated based on results in Cycle 1 to 3. ECGs will also be obtained

Clinical Trial Protocol BNT321-02

Page 18 of 127 Version: 2.0 Date: 22 JAN 2024

- prior to first BNT321 administration on Cycle 13, and at EOT and as clinically indicated during BNT321 monotherapy per assessment of the trial investigator. ECGs are performed as triplicate exams at all study timepoints per Section 8.3.3.
- 20. Complete blood count (CBC) with differential to include WBC, RBC, HGB, HCT, platelets, MCV, and MCH to be performed at screening, Day 1 of every cycle, EOT, at safety FU visit, and as needed according to investigator's discretion based on new symptoms and/or medical concerns.
- 21. Blood chemistry to include sodium, potassium, chloride, bicarbonate, blood urea nitrogen, creatinine, glucose, calcium, phosphate, magnesium, AST, ALT, total bilirubin, alkaline phosphatase, total protein, albumin, and uric acid to be performed at screening, Day 1 of every cycle, EOT, at safety FU visit, and as needed according to investigator's discretion based on new symptoms and/or medical concerns.
- 22. Serum amylase, -lipase and haptoglobin will be performed on Day 1 of every cycle and EOT, and as needed according to investigator's discretion based on new symptoms and/or medical concerns.
- 23. GGT will be performed at screening and on Day 1 of every cycle and as needed according to investigator's discretion based on new symptoms and/or medical concerns.

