- 12. Symptom-directed physical examinations will be performed on Day 1 of each cycle prior to treatment administration and at any visit where the patient indicates new symptoms that require evaluation or based on investigator's discretion.
- 13. Vital signs e.g., blood pressure, body temperature, heart rate, and respiratory rate will be performed prior to start of infusion. On non-treatment visits, vital signs will be performed once. Vital signs will also be performed at the safety FU visit.
- 14. Performance status must be recorded as ECOG and will be performed at screening and Day 1 of every cycle, at EOT, and as needed according to investigator's discretion based on new symptoms and/or medical concerns. Refer to the Appendix 1 for conversion between ECOG and KPS.
- 15. HRQoL will be performed at screening, Day 1 of every other treatment cycle starting from Cycle 3 to 12, at EOT and at every disease assessment (see Footnote 26 for timing of disease assessments).
- 16. Recorded from 21 days prior to the first administration of mFOLFIRINOX to EOT or safety FU visits. Includes prescription medications, over-the-counter medications, and supplements.
- 17. Adverse events will be collected and reported from the signing of the trial-specific ICF until safety FU.
- 18. ECGs will be performed at screening and on Day 1 of every cycle for C1 through C3. On these days ECGs are obtained prior to treatment, at t_{max}, and at end of last mFOLFIRINOX infusion. Investigators may obtain ECGs at additional timepoints in Cycle 4 to 12 if indicated based on results in Cycle 1 to 3. ECGs will also be obtained prior to first BNT321 administration on Cycle 13, and at EOT and as clinically indicated during BNT321 monotherapy per assessment of the trial investigator. ECGs are performed as triplicate exams at all study timepoints per Section 8.3.3.
- 19. Complete blood count (CBC) with differential to include WBC, RBC, HGB, HCT, platelets, MCV, and MCH to be performed at screening, Day 1 of every cycle, Week 25/EOT, at safety FU visit, and as needed according to investigator's discretion based on new symptoms and/or medical concerns.

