5.3 Exclusion criteria

A patient who meets any of the following criteria at screening will be excluded from trial participation:

- 1. Is pregnant or breastfeeding or planning pregnancy or to father children during the trial or within 60 days after last IMP treatment.
- A medical, psychological, or social condition which, in the opinion of the investigator, could compromise their wellbeing if they participate in the trial, or that could prevent, limit, or confound the protocol specified assessments or procedures, or that could impact adherence to protocol-described requirements.

Page 52 of 127 Version: 2.0 Date: 22 JAN 2024

- Had major surgery within 3 weeks of first dose of the trial treatment, where
 participation in the trial could compromise the patient's wellbeing in the opinion
 of the investigator.
- 4. Has abnormal electrocardiograms (ECGs) that are clinically significant, such as Fridericia-corrected QT prolongation >>470 msec (for women) and >450 msec (for men), (average of three ECGs at least 5 minutes apart).
- 5. Has a history of anaphylactic reaction to human, or humanized, antibody.
- 6. Have other known active cancer(s) likely to require treatment in the next 2 years.
- 7. Had prior radiotherapy or systemic treatment for PDAC.
- Active, uncontrolled bacterial, viral, or fungal infection(s) requiring systemic antiinfective therapy that has been administered less than 2 weeks prior to the first dose of BNT321.
- 9. Known hypersensitivity to any of the excipients of the experimental product BNT321.
- Known history of seropositivity for human immunodeficiency virus (HIV) with CD4+ T-cell counts <350 cells/μL and with a history of acquired immunodeficiency syndrome (AIDS)-defining opportunistic infections.
- 11. Known history/positive serology for Hepatitis B requiring active antiviral therapy (unless immune due to vaccination or resolved natural infection or unless passive immunization due to immunoglobulin therapy; patients with positive serology must have Hepatitis B virus viral load below the limit of quantification).
- 12. Active Hepatitis C virus infection (patients who have completed curative antiviral treatment with Hepatitis C virus viral load below the limit of quantification are allowed).
- Use of any IMP or device within 21 days before administration of first dose of trial treatment or ongoing participation in the active treatment phase of another interventional clinical trial.

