- 14. Is subject to exclusion periods from another investigational trial.
- 15. Are vulnerable individuals as per ICH E6 definition, i.e., individuals whose willingness to participate in a clinical trial may be unduly influenced by the expectation, whether justified or not, of benefits associated with participation, or of a retaliatory response from senior members of a hierarchy in case of refusal to participate.
- 16. Serum CA19-9 > 180 U/mL within 3 weeks of C1D1.
- 17. Incomplete macroscopic tumor removal (R2 resection).

Page 53 of 127 Version: 2.0 Date: 22 JAN 2024

- Significant cardiovascular risk (past medical history of coronary stenting or myocardial infarction within 6 months, or NYHA Class III/IV, heart failure, or concurrent unstable angina) or risk factors for QT prolongation (sustained Grade 3 or higher hypokalemia, history of unstable arrhythmia orfamily history of long QT syndrome).
- 19. Pre-existing neuropathy.
- 20. Homozygous UGT1A1*28 mutation, if testing required by local regulations.
- 21. Inflammatory disease of the colon or rectum, or occlusion or sub-occlusion of the intestine or severe post-operative uncontrolled diarrhea.
- 22. Complete dihydropyrimidine dehydrogenase (DPD) deficiency, if testing required by local regulations.
- 23. Received a live vaccine within 3 weeks prior to the first dose of trial treatment.
- 24. Patients with a contraindication to receiving mFOLFIRINOX.
- 25. Patients with active or latent tuberculosis or history of Mycobacterium tuberculosis infection currently or within the last 2 years.
- 26. Individuals committed to an institution by virtue of an order issued either by the judicial or the administrative authorities.

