6.1 Trial treatments administered

Name	mFOLFIRINOX	BNT321
Trial treatment type	Chemotherapy	Monoclonal antibody
Dosage form	NA	BNT321 is provided as a single-use glass vial containing 8.0 mL of sterile solution at 10 mg/mL in a buffer at pH 6.0, containing 25 mM histidine, 150 mM sucrose, 55 mM sodium chloride, and 0.02% polysorbate 80.
Unit dose strength(s)	 Oxaliplatin: 85 mg/m² Leucovorin: 400 mg/m² Irinotecan: 150 mg/m² 5-FU: 2400 mg/m²* 	0.5 CCI mg/kg based on cohort
Dosage regimen	mFOLFIRINOX will be administered on the first day of each 14-day cycle (i.e., C1D1, C2D1, C3D1, and so on for a total of 12 cycles) using the following dose and schedule for each agent: • Oxaliplatin: Day 1 • Leucovorin: Day 1 • Irinotecan: Day 1 (starting 30 minutes after leucovorin) • 5-FU: Day 1	BNT321 will be incorporated into the mFOLFIRINOX regimen starting from the second cycle and after the completion of the 5-FU infusion (e.g., initially on C2D3).
Diluent	mFOLFIRINOX is prepared and administered according to institutional standards, in compliance with the package insert for each drug	Prior to infusion, BNT321 is diluted in normal saline to obtain a final concentration of less than 5 mg/mL

BioNTech SE Confidential Page 55 of 127 Version: 2.0 Date: 22 JAN 2024

Name	mFOLFIRINOX	BNT321
Route of administration	 Oxaliplatin: IV over 2 hours Leucovorin: IV over 2 hours Irinotecan: IV over 90 minutes 5-FU: Continuous IV infusion over 46 hours, following oxaliplatin, leucovorin, and irinotecan 	IV infusion for 2 hours
Sourcing	See the Pharmacy Manual	See the Pharmacy Manual
Packaging and labeling	For details see the Pharmacy Manual	For details see the Pharmacy Manual

^{*} Reduced 5-FU dose may be implemented for patients with DPD deficiency, per the discretion of the treating physician. Abbreviations: 5-FU = 5-fluorouracil; CnDn = cycle number day number; DPD = dihydropyrimidine dehydrogenase; IV = intravenous; NA = not applicable.

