6.6.2 Randomization

For Phase II, part 2, patients will be randomized in a 1:1 fashion to one of two treatment arms, mFOLFIRINOX + BNT321 or mFOLFIRINOX alone. Randomization will be conducted in the trial's interactive web response system (IWRS) up to 3 days before Cycle 1 Day 1. Randomization will include stratifications to ensure balanced enrollment between the two arms for the following characteristics: tumor resection status (R0 vs R1) and tumor nodal status at resection (pN0 vs pN1).

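### Exclusion 8 counts its two-week anti-infective window back from the first BNT321 dose, so it cannot be assessed when eligibility is decided and is undefined for control patients; Table 2 footnote 17 uses the same anchor and gives the two arms unequal medication look-backs

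*Combined protocol and SAP*

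**What the plan says.** **Exclusion 8 (Section 5.3).** Infection requiring systemic therapy excludes a patient if that therapy was "administered less than 2 weeks prior to the first dose of BNT321". The lead-in to the list fixes when it is judged: "A patient who meets any of the following criteria at screening will be excluded from trial participation". The schedule of activities (Section 1.3) places screening before treatment: "Screening visit performed within 21 days prior to Cycle 1 Day 1".

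**Treatment start.** mFOLFIRINOX begins on C1D1 in both arms. BNT321 joins it "starting from the second cycle and after the completion of the 5-FU infusion (e.g., initially on C2D3" (Section 6.1), and in Phase II only in the combination arm. Cycles last 14 days. Section 6.6.2 has Phase II patients randomized "up to 3 days before Cycle 1 Day 1", and the schedule footnotes give Day -3 to C1D1.

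**Other timed exclusions.** Exclusions 3 (major surgery), 13 (prior investigational product or device) and 23 all count from the first trial treatment. The last reads "Received a live vaccine within 3 weeks prior to the first dose of trial treatment". Exclusion 16 (CA19-9) counts from C1D1.

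**Medication recording (Section 1.3).** For the combination arm, Table 2 footnote 17 says "Recorded from 21 days prior to the first administration of BNT321 to EOT or safety FU visits". For the control arm, Table 4 footnote 16 says "Recorded from 21 days prior to the first administration of mFOLFIRINOX to EOT or safety FU visits", and Table 1 footnote 17 (Phase I) uses the same start. Section 6.9 defines prior treatments by the 21 days before C1D1 for everyone, while Section 6.9.5 refers back to the schedule of activities for the period to be recorded in the eCRF.

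**The concern.** An exclusion criterion has to be decidable when the patient is admitted and, in a randomized comparison, has to mean the same thing whichever arm the patient will enter. Exclusion 8 is tied to a dose that lies in the future for every patient at screening and that half of the Phase II patients will never receive. A site that follows the text cannot apply the time limit before randomization and has no date to apply it to in the control arm. Section 5 prohibits eligibility waivers, so sites need a rule that they can apply as written.

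The stake is whether an infection exclusion works at the point where chemotherapy starts, and whether it works in the same way in both arms. The footnote raises a smaller, separate matter: two randomized arms with different stated look-back periods for prior medication.

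**Working it through.** The plan gives no figure of its own to reproduce; the check is calendar arithmetic. Take C1D1 as study day 1, with Day -1 the day before it.

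**1. First BNT321 dose.** With 14-day cycles, C2D1 = 14 + 1 = day 15 and C2D3 = 14 + 3 = day 17.

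**2. The window.** Less than two weeks before the dose means a gap of at most 13 days, so the window opens on day 17 - 13 = day 4 and runs to day 17.

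**3. Gap from each decision point to the dose.**
- C1D1: 17 - 1 = 16 days.
- Day -3, earliest randomization: 16 + 3 = 19 days.
- Day -21, earliest screening: 16 + 21 = 37 days.

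All exceed 13, so no day from screening to C1D1 falls in the window. An infection whose last anti-infective dose is on or before C1D1 is not caught by the time limit.

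**4. Sensitivity to scheduling.** Section 1.3 allows ±3 days on visits other than Day 3, and Phase II may move BNT321 to Day 1 after review of the Phase I safety data.

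| Cycle 2 case | First BNT321 dose | Days after C1D1 | Window opens |
|---|---|---|---|
| C2D3, Cycle 2 starts 3 days late | day 20 | 19 | day 7 |
| C2D3, on schedule | day 17 | 16 | day 4 |
| C2D1 dosing, on schedule | day 15 | 14 | day 2 |
| C2D3, Cycle 2 starts 3 days early | day 14 | 13 | day 1 (C1D1) |
| C2D1 dosing, 3 days early | day 12 | 11 | Day -2 |

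Only an early Cycle 2 visit brings the window back to C1D1 or before, and nobody knows at randomization that the visit will be early.

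**5. Control arm.** Under 1:1 allocation of 300 patients, 300 × 1/2 = 150 have no first BNT321 dose, so the window is undefined for them.

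**6. Comparison.** Counted from first trial treatment, as exclusions 3, 13 and 23 are, a window of the same length would run from Day -13 to C1D1. That lies inside the 21-day screening period and is the same in both arms. This shows what the other anchor would do; it is not a view on which washout is clinically right.

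**7. Footnote 17.** C1D1 is 16 days before C2D3, so recording from 21 days before first BNT321 reaches back 21 - 16 = 5 days before C1D1. With Day 1 dosing it would reach back 21 - 14 = 7 days. The control arm and Phase I have 21 days.

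**The case against.** The strongest reply is that infected patients are not unprotected at C1D1. Inclusion 8 requires fitness for chemotherapy, exclusion 2 leaves room for investigator judgment, and exclusion 24 bars anyone with a contraindication to mFOLFIRINOX. All apply before treatment and to both arms. This stands, and it limits the consequence. It does not repair the criterion, because none of the three sets an anti-infective window.

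A reader might infer that any patient still on anti-infectives at C1D1 gets through. The text does not support that. A combination-arm patient who continues therapy to day 4 or later does fall inside the window, although this becomes known only after randomization. A site could try to forecast it, but would have to guess both the course of therapy and the arm.

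A reader might also infer that infections let in this way bias the comparison of toxicity or dose intensity between arms. Infections present before randomization are allocated by chance, and the primary analysis includes all randomized patients (Sections 9.4 and 9.5.2). That objection succeeds.

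On footnote 17, a reader might infer that the washouts for investigational products, live vaccines and CYP3A4 or UGT1A1 agents go unchecked in the combination arm. They do not depend on the footnote: each keeps its own anchor in Section 5.3 or 6.9.1. Table 2 also marks concomitant medication at screening, before the arm is known, so actual collection may differ less than the footnotes state. What remains is an unequal written rule, which Section 6.9.5 makes the reference for eCRF recording.

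Finally, the protocol does not state what exclusion 8 was meant to protect against. A BNT321-specific purpose is possible, since exclusions 5 and 9 concern antibodies or BNT321. The sponsor may have had a reason for the anchor, but none is given.

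**Conclusion.** The point holds as a defect of anchoring. On the nominal schedule, exclusion 8's window covers days 4 to 17, after screening and, in Phase II, after randomization; it is undefined for about 150 of 300 randomized patients. The result rests on 14-day cycles and first BNT321 on C2D3, and changes only if Cycle 2 comes early.

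The randomization and control-arm parts concern Phase II only. In Phase I every patient is planned to receive BNT321, but the window still nominally falls after chemotherapy has begun.

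Separately, the stated medication look-back is about 5 days before C1D1 in the combination arm and 21 days in the control arm.

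How many patients either matter would affect cannot be derived from the documents. The neutropenia rates quoted in Section 2.3.2 are background rates from another trial and do not measure it. No differential bias in the primary DFS analysis is claimed.

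**What to change.** **Exclusion 8.** Reconcile its anchor with those of the other timed exclusions, so that the criterion can be evaluated before randomization and applies identically to both arms. The washout itself is for the sponsor to decide. If a BNT321-specific restriction is also intended, state it separately from eligibility.

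**Table 2 footnote 17.** Align the start of medication recording with Table 1 footnote 17, Table 4 footnote 16 and Section 6.9, so that both randomized arms have the same recorded look-back.

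**Cost.** Two wording edits in an amendment and no new procedure. A few patients with recent infections may start later or be rescreened, which Section 5.5 already permits.

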5.4 Lifestyle considerations

The sponsor foresees no particular lifestyle considerations for patients in this trial.

5.5 Screen failures

Screen failures are defined as trial patients who consent to participate in the clinical trial but are not subsequently entered in the trial or randomly assigned to trial treatment. A minimal set of screen failure information is required to ensure transparent reporting of screen failures to meet the Consolidated Standards of Reporting Trials (CONSORT) publishing requirements and to respond to queries from regulatory authorities. Minimal information includes demography, date of informed consent, screen failure details, eligibility criteria, and any SAE.

Screen failures may be rescreened two more times (for a total of three screenings per patient) at the investigator's discretion. Patients must re-sign the ICF prior to any rescreening. Rescreened patients will be assigned a new patient number.

5.6 Criteria for temporarily delaying enrollment or randomization

Enrollment or randomization may be paused or delayed if the SRC or independent data monitoring committee (IDMC) recommends a pausing of trial treatment according to Section 7.1.2.

Page 54 of 127 Version: 2.0 Date: 22 JAN 2024

6 TRIAL TREATMENTS AND CONCOMITANT THERAPY

Trial treatment is defined as any investigational treatment(s), marketed product(s) used as auxiliary medicinal product (AxMP) intended to be administered to a patient according to the trial protocol.

An "IMP" is any medicinal product which is being tested or used as a reference in a clinical trial (the tested product and its reference products, including placebos).

An "AxMP" is a medicinal product used for the needs of a clinical trial as described in the protocol, but not as an IMP (medicinal products used in the context of a clinical trial but not as investigational medicinal products).

Concomitant therapy is not considered trial treatment.

